To date, it is uncertain whether the use of antibiotics as prophylaxis before TACE is beneficial or not in the prevention of postoperative infection.

Excessive antibiotic use is a global problem and carries risks of adverse drug reactions like allergy or anaphylaxis, increased cost, and contributes to the emergence antimicrobial resistance [15, 16]. Therefore, it is the need of the hour to explore the utility of prophylactic antibiotics in TACE.

This study aims to determine the effectiveness of prophylactic antibiotic use for TACE and occurrence of postoperative liver abscess.

Methods

Inclusion Criteria:

- 1. Age 18 65 years
- 2. Diagnosis of primary liver cancer or hepatocellular carcinoma
- 3. Patients receiving TACE in PKLI & RC

Exclusion Criteria:

- 1. Receiving two or more TACE during the same hospitalization
- 2. Use of any antibiotics other than the prophylactic antibiotic in 48hours prior to TACE
- 3. Known hypersensitivity to specified antibiotic used in the study
- 4. Incomplete or missing laboratory investigations and data
- 5. Taking Sorafenib before TACE
- 6. TACE combined with ablation or immunetherapy
- 7. Tumor size >10 cm
- 8. Portal vein thrombosis
- 9. Dilated biliary channels on CT scan / Billiary invasion by tumor

Study Outcomes:

- 1. Predominantly neutrophilic leukocytosis ($> 11 \times 10^9$ /L) with fever (> 38 °C) in upto 48 hours post-TACE
- 2. Occurrence of liver abscess as diagnosed by imaging within 30 days of the procedure

3. Liver abscess requiring an intervention (e.g., percutaneous transhepatic abscess drainage (PTAD), percutaneous transhepatic abscess puncture or liver abscess incision) within 30 days of TACE

Sampling Technique:

In this study, consecutive sampling technique and randomization by lottery method will be applied. In lottery method the investigator will randomly draw numbers from the box to choose sample until the final sample size reaches. Two numbers will be assigned as '1' for antibiotic group and '2' for no antibiotic group.

Current standard of care treatment at PKLI&RC (as per local guidelines) would be given to all patients receiving TACE for the intervention group or 'antibiotic group' (i.e., Inj. Ceftriaxone 1g, intravenous × stat). While no antibiotic would be given to the 'no antibiotic group'.

Statistical analysis:

- 1. Data to be recorded on Excel sheet and subsequently exported to SPSS version 24 for further analysis.

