- 2. A univariate analysis will be employed for the comparison of variations in patients' baseline characteristics between the preventive medication group and the nonpreventive medication group. The Student's t-test will be employed to evaluate if the obtained data had a homogeneous variance and a normal distribution. For nonhomogeneous variance, the comparisons were made using a one-way analysis of variance (ANOVA). In order to compare categorical variables, Fisher's exact test or Pearson's 2 test was used as applicable.
- 3. The univariate analysis included chi-square tests for categorical variables and t-tests for continuous variables. Significant variables (P < 0.01) in univariate analysis and covariates considered clinically influential were then analyzed by multivariate stepwise logistic regression (forward stepwise logistic regression) to identify significant variables. We applied univariate and multivariate logistic regression models to estimate odds ratios (ORs) with 95% confidence intervals (CIs) for significant

- variables for finding potential risk factors in WBC> 11×10^9 /L group or postoperative infection group.
- 4. *P* value less than 0.05 was considered statistically significant.

References:

- Li B. Prophylactic Use of Antibiotics for Postsurgical Infection in c-TACE and DEB-TACE High-Risk Patients: A Case-Control Study. Journal of Healthcare Engineering. 2022 Apr 11;2022.

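### The analysis plan specifies no comparison of the randomised arms on any of the three Study Outcomes; its only outcome analysis is a risk-factor search that reports significant variables only

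*Combined protocol and SAP*

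**What the plan says.** All references are to the Combined protocol and SAP.

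- **Aim (end of the Introduction).** The effectiveness of prophylactic antibiotic for TACE and the occurrence of postoperative liver abscess.
- **Study Outcomes.** The first is a raised, mainly neutrophilic white count (above 11 × 10⁹/L) combined with a temperature over 38 °C in the first 48 hours after TACE. The second is "Occurrence of liver abscess as diagnosed by imaging within 30 days of the procedure". The third is an abscess that needs drainage or a similar procedure in the same 30-day window.
- **Statistical analysis, item 1.** Data entry and software.
- **Item 2.** A univariate comparison of "baseline characteristics between the preventive medication group and the nonpreventive medication group". It closes with a sentence on Fisher's exact or Pearson's test that opens "In order to compare categorical variables" and names no outcome.
- **Item 3.** Univariate chi-square and t-tests, then selection: "Significant variables (P < 0.01) in univariate analysis and covariates considered clinically influential were then analyzed by multivariate stepwise logistic regression". On reporting: "We applied univariate and multivariate logistic regression models to estimate odds ratios (ORs) with 95% confidence intervals (CIs) for significant" variables. The stated purpose is to find "potential risk factors in WBC> 11×10^9 /L group or postoperative infection group".
- **Item 4.** P below 0.05 is significant.

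**The concern.** A randomised trial answers its question by comparing the arms on its outcomes. None of the four items does this. The one comparison explicitly between arms concerns baseline characteristics, and the one analysis of outcomes asks which patient variables predict infection.

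Three consequences follow if the plan is carried out as written:

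- A non-significant antibiotic effect need not be reported on any stated outcome. The Introduction calls the benefit of prophylaxis uncertain and warns against excessive antibiotic use, so a null result is plausible and could matter for practice.
- An effect that is reported only because it was significant is biased away from the null.
- Without an estimate and interval, a non-significant result cannot separate no benefit from too few events. The Introduction puts abscess incidence at 0.1–4.5%, so few events are likely.

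The trial is also open-label. If the outcome, test and effect measure are not fixed in advance, they can be chosen with the results in view.

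**Working it through.** **Step 1. Outcomes against analysis.** The documents give no sample size, power or target effect, so there is no figure to reproduce. The main check is textual.

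| Study Outcome | Arm comparison specified? | Nearest text in Statistical analysis |
|---|---|---|
| 1. Neutrophilic leukocytosis with fever, up to 48 h | No | Item 3's WBC group, without the fever and neutrophil conditions |
| 2. Abscess on imaging, 30 days | No | None by name; *postoperative infection* is not defined |
| 3. Abscess needing intervention, 30 days | No | None by name |

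Arm could enter item 3's model as a clinically influential covariate and so avoid the P<0.01 screen. It would still face forward selection, and the significant-only rule for ORs covers both the univariate and the multivariable models.

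**Step 2. What the filter does (illustration).** Only the 0.1–4.5% incidence comes from the documents. Arm rates, arm sizes and the 80% power are assumptions.

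*(i) General exaggeration.* For a contrast with 80% power at two-sided 0.05, the expected z is δ = 1.960 + 0.842 = 2.802. With critical value c, and ignoring the negligible opposite tail, E(|Z| given |Z|>c) = δ + φ(c−δ)/Φ(δ−c).
- Filter at 0.05 (c = 1.960): 3.152, and 3.152/2.802 = 1.125.
- Filter at 0.01 (c = 2.576): 3.462, and 3.462/2.802 = 1.236.

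So the effect is overstated by about 12% or 24% on the z (log-OR) scale.

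*(ii) Chance that arm passes item 3's P<0.01 screen.* Power ≈ Φ{[d√n − 2.576√(2p̄(1−p̄))] / √(p₁(1−p₁)+p₂(1−p₂))}, where d = p₁ − p₂ and p̄ is their mean.
- 20% vs 10%, 200 per arm: (1.4142 − 2.576×0.5050)/0.5 = 0.227, giving 59%. With 100 per arm it is 27%.
- 4.5% vs 2.25%, 200 per arm: (0.3182 − 2.576×0.2554)/0.2549 = −1.33, giving 9%. With 100 per arm it is 4.5%.

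*(iii) Rare abscess, Fisher's exact P<0.05, by enumerating all binomial outcomes.*

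| Assumed rates | Per arm | Power | Need not be reported | Mean difference when P<0.05 | True difference | Ratio |
|---|---|---|---|---|---|---|
| 4.5% vs 0.1% | 100 | 27% | 73% | 7.05 points | 4.4 | 1.60 |
| 4.5% vs 0.1% | 200 | 85% | 15% | 4.79 points | 4.4 | 1.09 |
| 4.5% vs 2.25% | 200 | 15% | 85% | 4.97 points | 2.25 | 2.21 |

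**Step 3. What an interval adds.** Suppose 9/200 abscesses without antibiotic and 4/200 with it. Fisher's P = 0.26. The difference is 4.5 − 2.0 = 2.5 points. The Wilson limits are 2.39–8.33% and 0.78–5.03%. The Newcombe 95% limits are:
- lower: 2.5 − √[(4.5−2.39)² + (5.03−2.0)²] = −1.2 points;
- upper: 2.5 + √[(8.33−4.5)² + (2.0−0.78)²] = 6.5 points.

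A bare statement of non-significance would hide that the data fit no effect and also a reduction of up to 6.5 points.

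**The case against.** - **Item 2 may cover outcomes.** Its only named groups are the two medication groups, its closing sentence on categorical variables is not limited to baseline, and all three outcomes are binary. A sympathetic reader could take this as the arm comparison. That reading supplies a test at most: no outcome, no effect estimate and no interval.
- **Item 3 is not purely stepwise.** It also has univariate tests and models. This is right, and stepwise selection is only the last stage. The earlier stages serve the same risk-factor purpose, and ORs come under the same significant-only rule.
- **Abscess may be meant.** The Introduction links post-procedure infection with abscess, so *postoperative infection* might include it, and the WBC group might be shorthand for outcome 1. Both are possible. The fair statement is that outcomes 2 and 3 cannot be identified in the analysis, not that they were deliberately excluded.
- **The illustration is loose.** Fisher at 0.05 is not item 3's screen. The 4.5% vs 0.1% rows use the ends of a background incidence range as arm rates, which is an extreme contrast. The arm sizes are assumed, and the unreported share runs from 15% to 85% across the cases. All of this stands. The figures show how the rule behaves and do not predict this trial's result; the finding rests on the text.
- **The fix meets other gaps.** The exclusion for incomplete or missing laboratory data could remove patients after allocation, and an ordinary logistic model has no finite arm OR if one arm has no events. Both are fair and are addressed in the fix.

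**Conclusion.** The concern holds. No item names a between-arm test, effect measure or confidence interval for any of the three Study Outcomes, and the only outcome analysis reports ORs for significant variables. As written, the plan cannot be relied on to answer the trial's stated question, and it should be corrected before the data are analysed.

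The size depends on assumptions. In the assumed abscess scenarios, 15% to 85% of trials would be free not to report the effect, and significant results would overstate the true difference by 1.09 to 2.2 times. Low power itself comes from rare events and the unstated sample size. It is a separate matter that this correction does not change; the correction changes what is reported.

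**What to change.** Keep item 2 for baseline description and add text to this effect:

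> For each of the three outcomes exactly as defined under Study Outcomes, the arms will be compared as randomised, with an effect estimate (for example the risk difference), a 95% CI suited to rare events, and Fisher's exact P value, reported whatever the P value. A non-significant result will be interpreted from the CI and not as evidence of no benefit.

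Also:

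- State which outcome is primary. This is the investigators' decision; the aim points to liver abscess within 30 days.
- In any logistic model, force arm in and exempt it from selection. State a method for sparse data (for example penalised likelihood) in case an arm has no events.
- Label the stepwise search exploratory. Use the protocol-defined outcomes as its dependent variables, or define *postoperative infection*.
- Say how the missing-data exclusion applies after allocation, so that comparing the arms as randomised has a clear meaning, and report missing outcomes by arm.

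**Cost.** For the arm comparison, wording only, with no extra patients or data. Keeping patients who would otherwise be dropped for missing laboratory data may take some follow-up effort. The downside is that a wide interval will be shown openly. If abscess is named primary, the unstated sample size becomes a question of its own. For an assumed 4.5% vs 2.25%, 80% power and two-sided 0.05, n = [(1.960×0.2554 + 0.842×0.2549)/0.0225]², or about 1,011 per arm after rounding up from unrounded values.

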Title: Prophylactic antibiotic use in transarterial chemoembolization for hepatocellular carcinoma: an open-label, randomised, prospective study

Introduction:

Liver cancer especially hepatocellular carcinoma (HCC) is among the top five most common carcinomas in the world [1]. The treatment options for HCC includes surgery, liver transplantation, and radiofrequency ablation (RFA) with good survival rates. However, most HCC patients have angioinvasion. Furthermore, multiple lesions cannot be treated with such treatment strategies [2]. Image-guided transarterial chemoembolization (TACE) is accepted worldwide as a standard of care treatment for patients with hepatocellular carcinoma (HCC) in intermediate stage and good performance status [3]. TACE procedures, performed by the interventional radiologists, are minimally invasive with excellent outcomes as part of the nonsurgical treatment of HCC [1, 4]. Post-procedure-infection is uncommon but can lead to liver abscess and prolonged hospital stay. [7, 8] The chances of post-procedure-infection are higher in patients taking anticancer drugs due to immunosupression. [5, 6]. Incidence of liver abscess after TACE is 0.1 - 4.5% but carries a mortality rate of up to 50% [7, 8, 9].

TACE was linked to a risk of liver abscess. Prophylactic antibiotics pre-procedure lower this risk and ensuing surgical intervention [6]. Prophylactic antibiotics may not be required in TACE for HCC patients [10, 11, 12]. Moreover, old age, compromised hepatic function, hypoalbuminemia, portal vein cancer embolus, invasive procedures, using broad-spectrum antibiotics, and having diabetes mellitus are the independent risk factors for hospital-acquired infections (HAIs) after TACE in patients with primary liver cancer [1, 13].

According to the latest Cardiovascular and Interventional Radiological Society of Europe (CIRSE) standards of practice guidelines (2021), routine antibiotic prophylaxis is not recommended [14]. However, prophylactic antibiotics are recommended in cases where there is a high risk of developing a liver abscess. These include biliary obstruction or the presence of a bilioenteric anastomosis. The choice of agent is dependent on the suspected path ogens (upper gastrointestinal tract flora) and consideration should be given to potential hepatotoxicity of each agent. In complex cases involving multiple organisms, antibiotic resistance, or allergies, consulting with a microbiologist may be beneficial [14].

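### With P < 0.05 as the only significance rule and 95% intervals planned only for significant risk factors, a non-significant abscess comparison would be reported without an interval and could not support omitting prophylaxis

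*Combined protocol and SAP*

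**What the plan says.** **Significance rule.** Statistical analysis, item 4, gives a single threshold: a P "value less than 0.05 was considered statistically significant". Sidedness is not stated. The other threshold in that section, "Significant variables (P < 0.01) in univariate analysis" (item 3), is a filter for entry into a stepwise model, not a rule for comparing the arms.

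**Comparison of the arms.** Item 2 plans the "comparison of variations in patients' baseline characteristics between the preventive medication group and the nonpreventive medication group". No test, estimate or interval is assigned to the three study outcomes by arm.

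**Intervals.** Item 3 plans odds ratios with 95% confidence intervals, but for significant "variables for finding potential risk factors in WBC" above the cut-off, or in the postoperative infection group.

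**Setting.** Under Sampling Technique in Methods: "Current standard of care treatment at PKLI&RC (as per local guidelines) would be given to all patients receiving TACE for the intervention group". That treatment is ceftriaxone, and the other arm receives no antibiotic. The Introduction states: "Incidence of liver abscess after TACE is 0.1 - 4.5% but carries a mortality rate of up to 50" per cent. After describing the risks of antibiotic overuse it concludes: "Therefore, it is the need of the hour to explore the utility of prophylactic antibiotics in TACE". The stated aim is the effectiveness of prophylaxis.

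**The concern.** The antibiotic is this centre's current practice, and the trial is motivated by overuse. A reader of the results will therefore ask what happens to abscess risk when the antibiotic is left out. A P value above 0.05 does not answer that. It says that a difference was not shown, not how large a difference remains possible.

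For a rare event the two are far apart. A small trial can easily give P ≥ 0.05 while the data remain compatible with an excess larger than the whole background rate. Without an interval the reader cannot see this. Abscess is named in the aim and underlies two of the three outcomes, and the protocol quotes a mortality of up to 50% for it.

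**Working it through.** **Inputs from the documents.** Abscess incidence 0.1% to 4.5% (Introduction); threshold P < 0.05 (item 4); Fisher's exact test named for categorical variables (item 2). There is no sample size, power, effect size or margin, so the plan has no figure of its own to reproduce.

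**Assumptions.** 1:1 allocation; two-sided test; 100, 200 or 500 patients per arm; the quoted incidence taken as the risk without antibiotic; a true reduction of one half or three quarters. Fisher's test is the natural choice here: at 100 per arm, 4.5% and 2.25% mean only 4.5 and 2.25 expected events.

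**Step 1. How often is the test non-significant although the antibiotic works?**

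Power = Σ Bin(x; n, p₀) · Bin(y; n, p₁), summed over all pairs (x, y) with Fisher P < 0.05. Here p₀ is the risk without and p₁ the risk with antibiotic. The non-significant share is 100% minus power.

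| True risk, without → with | 100/arm: power, non-significant | 200/arm | 500/arm |
|---|---|---|---|
| 4.5% → 2.25% | 5.52%, 94% | 15.35%, 85% | 44.65%, 55% |
| 4.5% → 1.125% | 12.87%, 87% | 41.91%, 58% | 89.60%, 10% |
| 2% → 1% | 0.61%, 99% | 4.45%, 96% | 17.96%, 82% |
| 0.1% → 0.05% | 0.00%, 100% | 0.00%, 100% | 0.00%, 100% |

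At 50, 100, 200 and 500 per arm alike, if one arm has no abscess the other needs at least 6 for P < 0.05.

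**Step 2. What would a non-significant result leave open?**

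Newcombe's 95% interval for d = p̂₁ - p̂₂ (arm 1 without, arm 2 with antibiotic), with Wilson limits (l, u) for each arm:

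- lower = d - √[(p̂₁ - l₁)² + (u₂ - p̂₂)²]
- upper = d + √[(u₁ - p̂₁)² + (p̂₂ - l₂)²]

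*4/100 without, 2/100 with.* Fisher P = 0.68. Wilson limits are 1.57% to 9.84% and 0.55% to 7.00%; d = 2 points.

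- lower = 2 - √[(4 - 1.57)² + (7.00 - 2)²] = 2 - 5.56 = -3.6 points
- upper = 2 + √[(9.84 - 4)² + (2 - 0.55)²] = 2 + 6.01 = +8.0 points

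Miettinen-Nurminen gives -3.5 to +8.1. Either upper limit exceeds the top of the protocol's background range (4.5%).

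*2/100 without, 1/100 with.* P = 1.0; interval -3.7 to +6.1 points by either method.

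*0/100 in both arms.* The Wilson upper limit is z²/(n + z²) = 3.84/103.84 = 3.7%, so an excess of 3.7 points is still not excluded.

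**Step 3. Does this extend to outcome 1?** Not necessarily. The rate of leukocytosis with fever is not stated. If it were 20% to 40% (assumption), Fisher power for a halving would be 44% to 84% at 100 per arm and 77% to 99% at 200 per arm.

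**The case against.** Several objections have weight.

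- **The documents never say that a null result will be read as permission to omit prophylaxis.** A reader might infer this from the overuse rationale, but it is only an inference. The aim is worded as effectiveness, the antibiotic arm is labelled the intervention group, and a test of difference is coherent for that aim. The Introduction cites evidence on both sides, and the guideline it cites does not recommend routine prophylaxis, so the standard withheld is a local one. This stands.
- **A null result is not near-certain.** A reader might infer that it is, but that depends on a sample size the documents do not give. With 500 per arm and a three-quarters reduction from 4.5%, only about 10% of trials would be non-significant. No primary outcome is named, and the first one listed may be common. This stands, so the claim must be conditional.
- **Item 4 is a general threshold, not a decision rule for the arms.** The word superiority does not appear, and no outcome analysis by arm is specified at all. This is correct, but it widens the gap: nothing else in the plan supplies an interval for the arm difference.
- **The arm could enter the risk-factor model as a clinically influential covariate and so obtain an interval.** That is possible, but the intervals there are for significant variables, so a null arm effect would still have none. The model also concerns raised white cells or postoperative infection, with abscess not named.
- **A non-inferiority margin would change the question.** This stands. A margin is a trade-off for the sponsor and does not follow from the stated aim.

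**Conclusion.** The concern holds in a limited form. The plan asks for no interval on a non-significant arm difference, and for abscess a bare P ≥ 0.05 would be close to uninformative at modest size. At an assumed 100 to 200 per arm, about 94% to 85% of trials would be non-significant even if the antibiotic halved a 4.5% risk, and the share is higher at lower rates. An illustrative null result at 100 per arm leaves an excess of about 8 points open, and even no events in either arm leaves 3.7 points open.

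The percentages rest on the assumed sample size, 1:1 allocation, a two-sided Fisher test and the assumed reductions. They do not carry over to large trials with large effects, or necessarily to outcome 1. The need for an interval does not depend on them. The documents do not support the stronger claims that a null result is assured, that the sponsor will treat it as proof, or that the trial must be a non-inferiority trial.

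**What to change.** Add to the Statistical analysis section:

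1. For each of the three outcomes by randomised arm, and in particular abscess within 30 days, report events and patients per arm and the risk difference (no antibiotic minus antibiotic). Give a 95% Newcombe or Miettinen-Nurminen interval whatever the P value.
2. State that P ≥ 0.05 is not evidence that prophylaxis can be omitted, and that a null result with a wide interval will be reported as inconclusive.

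This takes a few sentences, no additional patients and no change to treatment. The price is that an uninformative null result must be described as such. The interval does not make a small trial precise, and the planned number per arm still has to be stated.

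A non-inferiority margin is needed only if the sponsor intends to claim that omission is acceptable. In that case the sponsor should set and justify it against the assumed event rate before the data are seen. The cost could then be large. As an illustration only, since the documents give no margin, take a 3-point margin, equal true rates, 80% power and one-sided 0.025. Then n per arm = (1.96 + 0.84)² × 2p(1 - p)/0.03², which is about 173 at 1%, 342 at 2% and 750 at 4.5%.

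### Three outcomes, no primary and one unadjusted 0.05 threshold: the chance of a false positive is not held at 5%, and a 48-hour fever result could stand in for abscess

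*Combined protocol and SAP*

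**What the plan says.** The aim, at the end of the Introduction, reads: "This study aims to determine the effectiveness of prophylactic antibiotic use for TACE and occurrence of postoperative liver abscess". It names abscess but does not call it primary.

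Study Outcomes then gives three numbered endpoints without ranking them:

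- Outcome 1: "Predominantly neutrophilic leukocytosis" together with fever, up to 48 hours after TACE.
- Outcome 2: "Occurrence of liver abscess as diagnosed by imaging within 30 days of the procedure".
- Outcome 3: "Liver abscess requiring an intervention", also within 30 days. It is by definition a subset of outcome 2.

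Statistical analysis has four items. Item 2 compares baseline characteristics between the groups and says of categorical variables that "Fisher's exact test or Pearson's 2 test was used as applicable". Item 3 describes a risk-factor screen feeding a stepwise logistic regression. Item 4 gives the only general criterion: a P "value less than 0.05 was considered statistically significant". No item sets a testing order, a hierarchy or an adjustment, and none writes out an arm-versus-arm test of any of the three outcomes.

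**The concern.** With three endpoints, one general threshold and no primary, nothing in the plan prevents significance on any one of them from being reported as the antibiotic working. Two things are at stake.

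The first is error control. Several tests at 0.05 together give more than a 5% chance of at least one false positive, unless the extra tests almost never reject.

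The second is what the conclusion rests on. Outcome 1 is an early clinical and laboratory sign, whereas outcomes 2 and 3 are imaging-confirmed abscess. A trial that was positive on outcome 1 and null on abscess could be presented as answering an aim that names abscess. The study is open-label, so a deciding outcome fixed in advance matters all the more.

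**Working it through.** The plan states no familywise error rate, sample size or power, so there is no figure of its own to reproduce beyond the 0.05 threshold.

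**Inputs from the documents**

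- Threshold 0.05 (Statistical analysis, item 4).
- Three outcomes, with outcome 3 nested in outcome 2 (Study Outcomes).
- Abscess rate: "Incidence of liver abscess after TACE is 0.1 - 4.5" percent (Introduction).
- Fisher's exact or Pearson chi-square for categorical variables (item 2).
- Two arms: "Two numbers will be assigned as '1' for antibiotic group and '2' for no antibiotic group" (Sampling Technique).

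**Assumptions, because the documents are silent**

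- Equal allocation and 100 to 400 patients per arm.
- Outcome 1 rate of 15% to 30%.
- 60% of abscesses need intervention.
- 60% of abscess patients also meet outcome 1.

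**Step 1: reference values.** Three independent tests give 1 − 0.95³ = 0.1426, or 14.3%. Two give 1 − 0.95² = 0.0975. The limit under any dependence is 3 × 0.05 = 0.15.

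**Step 2: nesting, large samples.** A correlated-normal calculation takes outcome 1 as independent and sets the correlation between outcomes 2 and 3 to the square root of the share of abscesses needing intervention. The error is 0.136 at a share of 25%, 0.129 at 50%, 0.120 at 75%, 0.111 at 90% and 0.097 at 100%. Nesting lowers the total but does not bring it back to 0.05.

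**Step 3: rarity and choice of test.** With few events the two tests behave differently. For a 4-to-0 split of abscesses in equal arms, Pearson gives χ² = 4²/[4(1 − p)], where p is the pooled event rate. This is just above 4 and exceeds the critical value 3.84. Fisher gives about 2 × 0.5⁴ = 0.125. Fisher needs a 6-to-0 split: 2 × 0.5⁵ = 0.0625, but 2 × 0.5⁶ = 0.031. The answer therefore depends on which test is used and how many abscesses occur.

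**Step 4: simulated null trials under the assumptions above.** Chance of at least one P < 0.05:

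| Tests used | Abscess 2% to 4.5% |
|---|---|
| Pearson on all three | about 9.5–12.5% |
| Fisher when expected counts are small, otherwise Pearson | about 5.5–12.5% |
| Fisher on all three | about 3.6–9.4% |

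At 0.1% abscess the total is about 5% or less whichever test is used. Even at 400 per arm only 400 × 0.001 = 0.4 abscesses are expected in each arm, so the abscess tests almost never reject.

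The middle row depends on arm size. A separate run of 8,000 trials per cell has simulation error up to about 1.96 × √(0.12 × 0.88/8000) = 0.007. It gave:

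| Per arm | Abscess 2% | Abscess 4.5% |
|---|---|---|
| 100 | 5.2–5.9% | 7.7–8.0% |
| 200 | 7.5–7.8% | 11.4–12.2% |
| 400 | 10.9% | 12.7–12.8% |

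**Step 5: where the false positives fall.** At 0.1% abscess, 98% to 100% of them are on outcome 1. With Pearson at 2% to 4.5%, about 60% of false-positive trials are not significant on outcome 2.

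**The case against.** The strongest reply has four parts.

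- **No outcome test is written.** Item 2 concerns baseline characteristics, item 3 concerns risk factors, and item 4 is a generic threshold. This stands. Testing each outcome at 0.05 is an inference, though the natural one, and the missing between-arm analysis is itself a gap.
- **The inflation may be small.** A reader might infer that the error rate is roughly doubled. The documents do not support that as a general figure. Item 2 allows Fisher's test where applicable, and Fisher throughout can leave the total below 5%. The stated abscess range starts at 0.1%, where there is essentially no inflation. The exclusions for dilated bile ducts and biliary invasion also make the upper end of that range less likely. Nor is 14.3% the trial's error rate: it assumes independence, which the nesting of outcome 3 rules out.
- **The figures are two-sided.** They count results in either direction. False claims of benefit are about half as frequent: 5.0–6.5% with Pearson throughout at 2% to 4.5% abscess, against 2.5% for a single two-sided test. This stands, although the relative inflation is unchanged.
- **The choice of primary belongs to the investigators.** The aim also speaks of effectiveness in general, and the Introduction frames the uncertainty as one about postoperative infection. That is fair, and it is a reason to settle the choice in the plan.

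None of this supplies a primary outcome or a testing rule. Where rarity removes the inflation, the second problem is at its worst, because almost any false claim would then rest on outcome 1.

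**Conclusion.** The concern holds in a conditional form. The plan names no primary outcome and has no multiplicity rule, so on the natural reading of item 4 the chance of at least one false positive is not guaranteed to be 5%.

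The size runs from no inflation (abscess near 0.1%, or Fisher throughout with small arms) to about 12.5% (Pearson, 4.5% abscess, large arms). These figures rest on assumed values for sample size, outcome 1 rate, intervention share and overlap, so no single multiplier should be quoted.

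The part that needs no assumption about rates is that a significant 48-hour fever and leukocytosis result could, on its own, be presented as the trial's answer. A reader might go further and infer that the investigators intend to choose the outcome after seeing the data. The documents do not say so; they only leave it open.

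**What to change.** In Study Outcomes and item 4 of Statistical analysis:

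1. Name outcome 2, liver abscess within 30 days, as the single primary outcome. Compare it between arms at two-sided 0.05 with a test valid for rare events (Fisher's exact test when expected counts are small).
2. Make outcomes 1 and 3 secondary, reported as between-arm differences with 95% confidence intervals and not used alone to claim effectiveness.
3. If the investigators want outcome 1 to be confirmatory as well, apply Holm to outcomes 1 and 2: the smaller P value is tested at 0.05/2 = 0.025 and, if that succeeds, the other at 0.05. Outcome 3 stays descriptive.

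With a valid test, either route holds the confirmatory error at or below 5%.

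The change is a few sentences and needs no extra patients in itself. It has two costs. A positive result on outcome 1 alone no longer proves benefit, or must meet the Holm threshold. Power on a rare primary event may also be low. With Fisher's test, power to detect a halving from 4.5% is about 15% at 200 per arm and 36% at 400; from 2% it is about 4% and 13%. A non-significant primary result must therefore be reported with its confidence interval and not as evidence of no effect.
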